8.1 Inclusion criteria at consent

- Resident in a care home for 24 hours or more, with a minimum planned period of residential care of 1 month.
- Able to provide informed consent or have a personal legal representative who can provide consent for inclusion.
- If the SU takes a regular probiotic but chooses to discontinue the probiotic

8.2 Exclusion criteria

- Severely immuno-compromised, e.g. known severe neutropenia
- Has artificial heart valve in situ.
- Medical history of acute pancreatitis.
- Requires naso-jejunal feeding /nasogastric feeding Currently has a colostomy.
- SU without capacity already receiving a probiotic

9 Recruitment and randomisation of Service Users

Following site initiation, the care home will aim to enrol all eligible SUs at that site. At this point, SUs (or their representatives) will be asked to provide consent to be monitored for up to one year and to be randomised to receive probiotic or placebo should they be prescribed antibiotics for acute infection in the course of routine care during this period.

There are likely to be two types of SUs who are eligible to join the study; those who have capacity and are able to consent for themselves and those unable to consent for themselves (lack capacity). Consent procedures will differ according to the mental capacity of the SU. ICH GCP trained senior care home staff/care home nursing staff or trained PAAD study RNs, will be responsible for consenting SUs or their personal/professional legal representatives.

9.1 Mental Capacity Assessment

Mental capacity will be assessed according to the Mental Capacity Act 2005, which provides a legal framework within which health and care professionals must act. As such all care homes have senior staff members who are fully trained to assess the mental capacity of SUs at any time. This Code of Practice provides comprehensive advice on good practice for the assessment of capacity, and depends on clinical judgement within a valid contestable process.

According to the Mental Capacity Act, the SUs will be presumed to have capacity, unless there is any reason to doubt their mental capacity. In the event that there is any doubt raised by the care home staff or the researchers, the SU will be assessed for mental capacity by the PAAD senior RN or the senior care home staff. A standard template for recording of the mental capacity assessment will be provided to care homes, together with specific training on the use of this template to the senior care home staff. This document will be reviewed by the PAAD RNs or senior care home staff to enable a decision to be made regarding the mental capacity of the SU, prior to taking consent from the SU or their legal representatives.

9.2 Cooling- Off period

During the recruitment period of PAAD Study Stage 1, the care homes as study sites reported that relatives/consultees wished to sign the "consultee declaration of assent form" on the day that they were provided with the information about the study. Some relatives did not wish to wait for 48 hours before making a decision, as they felt they had considered all the issues, had access to sufficient information and all their questions had already been answered. Many visited the care home infrequently, and so a period of enforced delay would limit the SU's opportunity to participate in research. Enforcing a pre-determined 'cooling off' period, irrespective of the time required by the person providing consent/assent for this study was considered patronising by many relatives. They preferred to be able to provide consent/assent at the point they felt ready to do so.

The Information Sheet for personal/legal representatives can be sent by post, however a face-to-face discussion for informing the relative is the method of choice in many care homes. Furthermore due to the type of IMP under investigation (Type B according to the risk adapted approach to conducting IMP trials), it was considered that for SUs with full capacity and legal representatives of SUs without full capacity should be given as much time as they require. This period of time could mean providing consent on the same day or after as much time as required to obtain informed consent.

9.3 Number of participants

In order to reach our target of 400 randomised service users, we estimate 1214 SUs will need to be approached to take part in the PAAD study and 607 SUs will need to be recruited to the enrolment stage by obtaining advanced consent.

9.4 Recruitment process

There are two stages to recruiting SUs to the study:

The first stage is the enrolment stage (see section 9.5). All eligible SUs in care homes can enrol and provide consent to take part in the study. CHS, nursing staff, PAAD Study RNs or the Research Officers (ROs), who are trained to take consent, will identify those SUs who are potentially eligible to join the study. There will be two types of participants within this study those with capacity (see section 9.5.1) and those without capacity (9.5.2) and the recruitment process will differ accordingly.

The second stage is the randomisation stage (see section 9.6), which occurs when an enrolled SU is prescribed an oral antibiotic. At this stage, the GP will re-assess the SU to ensure that they still meet all of the eligibility criteria.

9.5 Informed consent

Informed consent must be taken by suitably qualified, experienced and trained personnel in accordance to the ICH GCP directive on taking consent and before any study related procedures are undertaken. Written informed consent will be obtained from the SU or their personal (a person not connected with the conduct of the study, who is suitable to act as the legal representative by virtue of their relationship with the adult and available and willing to do so, i.e. next of kin, those who visit most regularly)/professional (a person not connected with the conduct of the study who is: (a) the doctor primarily responsible for the adult's medical treatment, or (b) a person nominated by the relevant health care provider (e.g. an acute NHS Trust or Health Board)) legal representative.

Prior to consenting to take part in the study, all SUs or their personal legal representatives, will be notified that they can withdraw their consent at any time during the study period. The SU/representative will be allowed as much time as needed to consider the information, and the opportunity to question the CHS, study RNs, ROs, their GP or other independent parties to decide whether they will participate in the study.

The following information sheets and consent forms will be provided to the care homes:

Service user

- 1) SU information sheet (SIS)
- 2) SU user consent form

Service user's representative

1) Detailed personal /professional legal representative information sheet

- 2) Personal / professional legal representative consent form
- 1) Verbal Consent Form for SUs or personal/professional legal representatives

In the event that a SU requires a more accessible information sheet this will be provided using either:-

- a) a simplified pictorial version of the study information sheet interpretation by sign language for the hard of hearing
- b) translation of the information into Welsh or an ethnic minority language

9.5.1 SU with Mental Capacity

According to the Mental Capacity Act, all SUs will be presumed to have capacity, unless there is any reason to doubt their mental capacity. If the SU has capacity, the person taking consent will provide the SU with written and verbal information about the study, ensuring that the information is fully understood. Understanding and consent will be checked by asking the SU to repeat back important aspects of the study. If they are happy to participate, SUs with capacity will be asked to sign and date the consent form, which will be countersigned and dated by the senior care home staff/nursing staff or RN taking consent. A copy of the signed Informed Consent form will be given to the SU and the original signed form will be retained at the study site. The SU's GP will be informed that they are taking part in the study.

9.5.2 SU without mental capacity

If the person taking consent makes the assessment that the SU lacks mental capacity, a standard template for recording of the mental capacity assessment will be completed. They will then liaise with the senior care home staff or nursing staff to identify a personal legal representative. In the event that a personal legal representative cannot be contacted by telephone or are themselves without capacity, the SU's professional legal representative will be contacted for consent. The SU's professional legal representative must not be the SU's own GP, if that GP is involved in the running or management of the care home.

The SU's personal/professional legal representative will be provided with information about the study and will be asked whether or not the SU would want to join the study. The personal/professional legal representative will then be asked to provide consent on

PAAD Stage 2 RCT Protocol, Version 4.1, 07/09/2012

behalf of the SU to join the study. The care home staff will inform any other relevant persons who need to be informed, e.g. SU's Social Worker or Case Manager, i.e. traditional professional social carers, as currently defined within social care. If they are happy for their relative (the SU) to participate, they will be asked to sign and date the consent form, which will be countersigned and dated by the senior care home staff/nursing staff or RN taking consent. A copy of the signed Informed Consent form will be given to the personal/professional legal representative and the original signed form will be retained at the study site. Since some personal legal representatives may not be able to attend a face-to-face interview for the consenting procedure, these documents may be sent by post from the care homes. The care home senior staff/RN or ROs will countersign signed and dated consents returned by the personal/professional legal representatives and a copy of the completed consent form will be sent to the personal/professional legal representative. The original consent document will be retained at the study site.

If the personal/professional legal representative wishes to provide consent immediately after receiving the information sheet on the study, they will be able to do so. All legal representatives who have not responded will be contacted by phone at least once by the CHS, the study RN or by ROs.

In the event that a personal/professional legal representative themselves loses capacity or dies during the study period, an alternative personal/professional legal representative will be contacted. If there is no one to represent the SU in the study, the SU will be excluded.

If the SU's own GP is the designated professional legal representative, an alternate GP within the same general practice, who is not involved in the conduct of the study, or the running or management of the care home, will be asked to act as their professional legal representative.

9.5.3 Verbal consent

In the event that a SU with capacity or a legal representative for a SU without capacity cannot provide handwritten signatures on the consent document, a verbal consent will be taken. In such cases, one of the senior CHS will read and discuss the study with the SU or their legal representative to ensure understanding of the study protocol. A member of the Research Team will witness, sign and date the consent document to approve that consent has been given.

9.6 Randomisation and unblinding

Randomisation will be coordinated centrally by SEWTU. The trial statistician will produce the main randomisation list. SEWTU will provide SMPU with a list of random allocations numbers linked to either placebo or probiotic, which will be used to label the study medication packs. Each medication pack will be labelled with a unique identification number (study medication pack number). This study is a double blind trial therefore, the SUs, consultees, care home staff nor the PAAD study team will be aware of the treatment allocation. The unique identification number on each study medication pack will be linked to the randomisation file, which will only be accessible by the trial statistician.

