9.6.1 Allocation of Study Medication

Once an antibiotic for an acute infection has been prescribed to a SU who has provided advanced consent to participate in the study, the SU will be re-assessed against the following exclusion criteria. All criteria must be answered no for a SU to be allocated study medication (i.e. randomised)

Exclusion criteria

- Previously been allocated study medication
- Service User's stool pattern is diarrhoea (defined as 3 or more stools at BSC type 5-7 within 24 hours)
- Severely immuno-compromised, e.g. known severe neutropenia
- Has artificial heart valve in situ.
- Medical history of acute pancreatitis.
- Requires naso-jejunal feeding /nasogastric
- Currently has a colostomy.
- SU is taking a probiotic on a regular basis and is unwilling to discontinue use.

General Practitioners (GPs), visiting their SU, will assess the SU for Eligibility for Study Medication CRF to re-confirm their eligibility at the same time as they prescribe the antibiotic(s). In the event that re-confirmation of eligibility and randomisation authorisation has not been obtained at the time of GP visit, the CHS will be trained and encouraged to alert the researchers by telephone or by fax within 24 hours of the SU being issued with a prescription. The RNs may assess eligibility; however the final approval for randomisation of the SU will be from a responsible clinician at the SU's general practice obtained either by fax from the RN or by a personal visit by a researcher to the GP surgery. When the SU has been confirmed as eligible, the next sequentially numbered study medication pack will be allocated to the SU.

In the event that the researchers cannot obtain GP approval for randomisation and prescription completion for the study medication within 72h, the SU will be monitored until such time they are prescribed a further antibiotic. At this time point the same procedure as described above will be followed.

9.6.2 Unblinding participants.

In the event that the SU needs to be unblinded the care home staff are directed to contact the PAAD team on [name]. The PAAD unblinding SOP will be followed to un-blind the participant and in this case the un-blinding of randomised SUs can only be carried out by the QA Manager at SEWTU.

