15.3 Data storage & retention

All data will be kept for 15 years in line with Cardiff University's Research Governance Framework Regulations for clinical research. This data will be stored confidentially on password protected servers maintained on the Cardiff University Network.

Electronic data will be stored on fire-walled University computers, and only accessible to researchers involved in the study. All procedures for data storage, processing and management will be in compliance with the Data Protection Act 1998. All paper records will be stored in a locked filing cabinet, with keys available only to the trial management team. The Trial Statistician will carry out analysis. All essential documents generated by the study will be kept in the trial master file.

16 Study closure

The end of the study will be considered as the date on which the last participant has completed their follow-up assessment.

For the purpose of regulatory requirements the end of the study is defined as the end of the follow-up period of the last recruited SU. For the purpose of the research ethics committee the study end date is deemed to be the date of last data capture.

17 Regulatory and ethical issues

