18.2 Trial Management Group

The TMG will consist of the Chief Investigator, Co-Applicants, a member of the CHS, a lay representative, TM, Trial Statistician and Trial Administrator. The role of the TMG will be to help set up the study by providing specialist advice, input to and comment on study procedures and documents (information sheets, protocol, etc). They will also advise on the promotion and running of the trial and deal with any issues that arise. The group will meet monthly throughout the course of the study.

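### The study team is declared blind, yet the trial statistician, who sits on the TMG and does the analysis, makes the list and is the only one given access to the randomisation file; the sole authorised unblinder is a different person

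*Protocol*

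**What the plan says.** Four places in the protocol assign the relevant roles.

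- **Section 9.6, list and file.** "The trial statistician will produce the main randomisation list". The pack numbers are then "linked to the randomisation file, which will only be accessible by the trial statistician".
- **Section 9.6, blinding.** The trial is double blind, and the protocol says of those involved that neither "the SUs, consultees, care home staff nor the PAAD study team will be aware of the treatment allocation". It makes no exception for the statistician.
- **Section 9.6.2, unblinding.** The care home contacts the PAAD team, an unblinding SOP is followed, and "un-blinding of randomised SUs can only be carried out by the QA Manager at SEWTU". The SOP is not reproduced.
- **Sections 15.3 and 18.2, the statistician's other roles.** "The Trial Statistician will carry out analysis", and the TMG includes "a lay representative, TM, Trial Statistician and Trial Administrator". That group meets monthly, advises on the conduct of the trial and handles problems as they come up.

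Section 9.6 also has SEWTU send the packing unit (SMPU) a list linking numbers to treatment, for labelling the packs.

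**The concern.** One role generates the allocations, has sole access to the key, takes part in monthly trial management and analyses the data. The protocol nevertheless says without qualification that the study team is blind. If the statistician belongs to that team, the statement is untrue as written. If not, the protocol should say so and state what protects the analysis.

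At stake is whether the double-blind claim reaches past data collection. Some judgement remains after the stool charts are in. For example, the primary outcome in section 14.2 requires normal stools beforehand but gives no length for that period. Whoever settles such points should not have the arm labels to hand, and the protocol should let a reader see that they do not.

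The second issue is one of fit. Authority to unblind is given to one person, and the only file the protocol names for tracing a pack to its arm is reserved to another.

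**Working it through.** No arithmetic applies: no sample size, power or error rate enters this point. The check is to set the sentences side by side.

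| Question | Answer in the protocol | Section |
|---|---|---|
| Who generates the list? | Trial statistician | 9.6 |
| Who can open the randomisation file? | Trial statistician only | 9.6 |
| Who is blind? | Residents, consultees, care home staff, PAAD study team | 9.6 |
| Who analyses? | Trial statistician | 15.3 |
| Is the statistician part of trial management? | Yes, a TMG member | 18.2 |
| Who may unblind? | SEWTU QA Manager only | 9.6.2 |
| Is a separate unblinded statistician, firewall or masked coding described? | No | none |

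**Step 1: blinding.** Section 9.6 says that neither "care home staff nor the PAAD study team will be aware of the treatment allocation". The term for the team is not defined, so placing the statistician inside it is an inference. It is a strong one, because section 18.2 puts the role in the management group and section 15.3 gives it the analysis. On that reading, the blinding statement and the file-access statement in 9.6 cannot both hold.

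**Step 2: unblinding.** The word "only" restricts both file access (9.6) and unblinding authority (9.6.2), and the two restrictions name different people. Taken literally, the QA Manager is excluded from the file. An SOP that gave the QA Manager that same file would contradict 9.6. An SOP that used a different code-break source would not, but the protocol names no such source.

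**Step 3: can the allocations still be unseen?** Section 14.1 has the permuted blocks generated before the trial begins, and 9.6 says the trial statistician generates them. If this was done as described, the person due to analyse the data has already had the list. Moving the file later limits further access but does not undo that.

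**Step 4: accumulating data.** Section 15.1.2 plans no interim analysis. Section 18.4 has the IDMC monitor safety and benefit as data accrue, meeting annually. The protocol does not say who would prepare tables by arm if the committee asked for them. With file access as written, that could only be the trial statistician.

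**The case against.** The other side has a fair case in several respects.

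- **The blinding sentence may be a general rule with a stated exception.** It is followed directly by the sentence naming the statistician as file holder, and section 9.6.2 uses a similar team name for the group care homes telephone. This reading is possible, but the exception is not expressed, and nothing is then said about masking the analysis.
- **Important protections are in place.** Care home staff are blind, the placebo is matched, stool type and frequency are charted during follow-up, and packs are taken in sequence after GP approval with no part for the statistician. This stands. It confines the exposure to choices made after data collection.
- **The SAP may deal with the analysis.** Covariates are expressly left to it, and handling of incomplete charts and the timing of analyst unblinding commonly are too. This also stands. A reader might infer that analytic decisions will be taken with the arms in view. The protocol shows who can open the file, not that the file will be used for those decisions or that the analysis dataset will carry true arm labels.
- **The unblinding SOP may supply another source.** A reader might infer that an unblinding request could not be met, or that residents are exposed to a safety gap. The SOP is not available, so neither conclusion is supported. Only the mismatch in wording is.
- **The packing list is not a contradiction.** A reader might see the list sent to SMPU as breaching sole access. The restriction in 9.6 applies to the randomisation file, and a packer must know what goes into each numbered box. It does mean that the statistician is the only holder of the file, not of all allocation information.

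None of these points removes the conflict between the protocol's own sentences.

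**Conclusion.** The protocol contradicts itself on who is blind, and its rules on file access and unblinding authority do not fit together. Both should be corrected. This is a should-fix matter of trial governance; the design is not invalidated by it.

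Its size can be stated only in scope. The file covers all 400 planned allocations, and one role combines list generation, sole file access, TMG membership and analysis. A reader might try to size it by asking how few recoded residents would carry a borderline result across 5%. That would not measure this defect: any result near the threshold can be tipped by one event, whatever the blinding arrangement. No misuse is suggested.

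The conclusion assumes that the role named in 9.6, 15.3 and 18.2 is the same person, and that a TMG member who analyses the trial belongs to its study team. The unblinding part assumes nothing about the SOP beyond its absence from the protocol.

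**What to change.** 1. **Section 9.6, custody.** Let the QA Manager hold the randomisation file and code break, or a SEWTU person independent of the analysis if one is available. SMPU keeps its packing list.
2. **Section 9.6, masking.** State that the trial statistician works with masked arm codes until the SAP is signed off and the database is locked, and that any unblinded tables for the IDMC come from the file holder.
3. **If the list already exists.** If the trial statistician has generated it, disclose this and remove that person's access from then on.
4. **Section 9.6.2.** Name the code-break source the QA Manager uses, so that it agrees with 9.6 and the SOP.

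The cost is protocol wording, one transfer of file access and a small amount of unit time to prepare masked datasets and any IDMC tables. Because the QA Manager can hold the file, the change does not depend on finding another statistician. Sample size, visits and treatment are untouched. The limitation is that a statistician who has already produced the list cannot be made blind again, which is why disclosure is part of the fix.
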